4.3 Handling of Missing Data

In order to achieve the goal of a well conducted clinical trial according to ICH Good Clinical Practice (ICH-GCP), every effort should be made to collect all data. However, despite best efforts, it may be inevitable that missing or incomplete data are reported. All missing or partial data will be presented in the subject data listing, as they are recorded on the CRF. Except as noted, missing data will not be imputed or carried forward in any statistical analysis.

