4.3.1 Imputation rules

Unless otherwise specified data will not be imputed, and rules for imputation are specified in the dataset specification documents.

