- The first bone scan with ≥ 2 new lesions compared to baseline is observed < 12 weeks from randomization and is confirmed by a second bone scan taken ≥ 6 weeks later showing ≥ 2 additional new lesions (a total of ≥ 4 new lesions compared to baseline); or
- The first bone scan with ≥ 2 new lesions compared to baseline is observed ≥ 12 weeks from randomization and the new lesions are verified on the next bone scan ≥ 6 weeks later (a total of ≥ 2 new lesions compared to baseline).

The date of progression of bone disease will be the date of the first observed bone progression, not the date that confirmed the bone progression.

The date of radiological progression will be determined following the rules in [Table 9–6](#).

Radiological progression-free survival is defined for each comparison as the time (days) from the randomization baseline to the date of radiological disease progression or death from any cause (if death occurs without prior progression). See [Table 9–7](#) in Appendix 9.1.5 for detailed censoring rules for both Comparison 1 and Comparison 2.

If data permits, unconfirmed radiological progression-free survival and time to unconfirmed radiological progression will be analyzed as sensitivity analyses based on central reviewer. Bone progression in this case does not require confirmation.

Pain endpoints

The pain data collected from ePRO will be used for these analyses.

Worst pain score (WPS) at a given visit is defined for each subject as the mean of the 7 day “worst pain score” assessments taken on or before each applicable visit. If less than 4 non-

missing WPS values are available for a given visit, then the weekly worst pain score will be left missing for that visit.

Timepoint pain improvement rate is defined with respect to each applicable baseline as the proportion of subjects with a 30% and 2-point decrease in WPS with respect to the applicable baseline assessment over 2 consecutive assessment periods conducted at least 3 weeks apart among subjects with a WPS score ≥ 4 at the applicable baseline. The first of the 2 consecutive periods is taken to be the date of improvement.

Time to pain progression is defined for each comparison in subjects with a WPS of ≤ 7 at the applicable baseline as the time from the applicable start date to an increase of 2 or more points in WPS (with respect to the applicable baseline). Refer to

Table 9–4 in Appendix 9.1.3 for detailed censoring rules.

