Each subject will fill out the complete 11-question BPI-SF using an ePRO device at the Treatment Day 1 visit and at each clinic visit thereafter through Week 48. For subjects in Arm A and Arm B, the modified complete BPI-SF will also be filled out on the day of telephone contacts scheduled for Weeks 28, 32, 40, and 44. The data will be collected for one week (6 days prior to the applicable visit and the morning of the visit) prior to each clinic visit or phone call follow-up.

The BPI-SF (Protocol Section 14.9) is a short, self-administered questionnaire with 11 items, which was designed to evaluate the intensity of, and the impairment caused by pain. All BPI-SF items are scored using rating scales. Four items measure pain intensity (pain now, average pain, worst pain, and least pain) using 0 (“no pain”) to 10 (“pain as bad as you can imagine”) numeric rating scales, and seven items measure the level of interference with function caused by pain (general activity, mood, walking ability, normal work, relations with other people, sleep and enjoyment of life) using 0 (no interference) to 10 (complete interference) rating scales.

The items are aggregated into two dimensions, (1) **Pain severity index**, using the sum of the four items on the pain intensity, and (2) **Function interference index**, using the sum of the seven pain interference items (at least 4 out of 7).

Each BPI-SF subscale, and the two indices for pain severity and function interference, will be summarized using descriptive statistics.

Weekly Average pain score (APS) is defined for each subject at baseline and at each post-baseline date, as the mean of the “average pain score” values in the last 24 hours from the preceding 7 days before each applicable visit or telephone contact per the BPI-SF.

Analysis of Exploratory Endpoints

Identical statistical methods for analyzing time-to-event secondary endpoints, as elucidated in section 6.2.2.2, will be applied to the analysis of time-to-event exploratory endpoints:

- Time to radiological bone progression
- Time to radiological soft-tissue progression
- Time to total alkaline phosphatase (ALP) progression
- Time to ALP progression without 12-week restriction
- Time to PSA progression
- Time to PSA progression without 12-week restriction
- Time to pain progression or increase in analgesic use following baseline
- Time to increase in analgesic use
- Time to increase in physical symptoms of disease based on FPSI-DRS-P

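### The BPI-SF function interference index may be scored from 4 of 7 items but is defined as a sum without proration, so partial forms fall on a shorter scale

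*SAP*

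**What the plan says.** SAP section 6.2.3.1.1, under BPI Subscales, forms two indices from the questionnaire. The function interference index is built "using the sum of the seven pain interference items (at least 4 out of 7"). Its items are rated "using 0 (no interference) to 10 (complete interference) rating scales", so a complete form runs from 0 to 70, and 0 is a real answer. The pain severity index is built "using the sum of the four items on the pain intensity", with no allowance for partial completion.

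On missing data, section 4.3 states: "Except as noted, missing data will not be imputed or carried forward in any statistical analysis". Section 4.3.1 adds: "Unless otherwise specified data will not be imputed, and rules for imputation are specified in the dataset specification documents". The main SAP notes no exception for the BPI-SF, and neither supplemental SAP (2 July 2018 and 8 October 2018) contains a BPI-SF scoring rule.

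On use, section 6.2.3.1.1 says: "Each BPI-SF subscale, and the two indices for pain severity and function interference, will be summarized using descriptive statistics". The analysis part of the same section lists both indices among the variables described by timepoint.

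**The concern.** A threshold of 4 answered items makes sense only together with a score that does not depend on how many items were answered, such as a mean or a prorated sum. Here the threshold is attached to a plain sum. Two subjects with the same interference per item then receive different scores because one of them left items blank, and the two scores enter the same mean, median and range.

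The error has one direction: a partial sum can only equal or fall below the full sum. If completeness fell during follow-up, part of the shift would look like improvement. If it differed between arms, part of the shift would look like a treatment difference.

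**Working it through.** The SAP states no figure on this point, so there is none to reproduce. The check is direct arithmetic.

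**Inputs from section 6.2.3.1.1:** seven items, each 0 to 10; aggregation by sum; at least 4 items answered. **Input from section 4.3:** no imputation unless noted.

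**Formulas.** Let k be the number of answered items (4 to 7) and s a common item score.
- Raw sum: k × s
- Prorated sum: (mean of answered items) × 7 = 7s
- Understatement: 1 − (k × s)/(7 × s) = 1 − k/7, whatever the value of s

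| Items answered | Maximum raw sum | Raw sum at s = 5 | Prorated sum at s = 5 | Understatement |
|---|---|---|---|---|
| 7 | 70 | 35 | 35 | 0% |
| 6 | 60 | 30 | 35 | 14.3% |
| 5 | 50 | 25 | 35 | 28.6% |
| 4 | 40 | 20 | 35 | 42.9% |

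**When item scores differ.** The shortfall against the full seven-item sum is the sum of the true values of the unanswered items. It can therefore be smaller or larger than the table shows. It is zero only if every unanswered item would have been rated 0.

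**Within one subject (illustrative scores).** A complete baseline form at 5 per item gives 35. Unchanged interference with 4 answers gives 4 × 5 = 20, an apparent improvement of 15 points. Worsening to 8 per item with 4 answers gives 4 × 8 = 32, still below 35, while the prorated value is 8 × 7 = 56.

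**At group level (assumed shares).** With an item mean of 5 and a share q of forms having exactly 4 answers, the mean falls by q × (35 − 20) = 15q.
- q = 5%: 0.75 points
- q = 10%: 1.5 points
- q = 20%: 3.0 points

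The SAP supports no particular q. These values show only how the bias scales.

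**Comparison within the SAP.** Section 6.2.2.1 takes the worst pain score at a visit as a mean of daily values and sets a minimum count of 4: if fewer "missing WPS values are available for a given visit, then the weekly worst pain score will be left missing for that visit". A mean with a minimum count is the form that the interference index lacks.

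**The case against.** The strongest reply is that the SAP never says that blanks score 0. A reader might infer such a rule, but the text does not contain one. It names a construct and a completeness threshold and is silent on how a partial form becomes a score. Proration may have been intended, and section 4.3.1 places imputation rules in dataset specifications that are not at hand. This stands as a limit on the claim: zero-scoring is the arithmetic consequence of following the text literally, not a stated rule. It does not remove the defect. The BPI paragraph does not refer to those specifications, and a sum followed literally under the no-imputation default gives the shorter scale. If proration was meant, the text still needs to say so.

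A second reply is that capture on an ePRO device may prevent skipped items. The SAP does not say so, and a 4-of-7 threshold presupposes that gaps occur. Even so, the number of affected forms is unknown and could be small.

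A third reply is that nothing depends on the index. That is correct. It is exploratory, is not tested, and feeds no primary or secondary endpoint. The secondary pain endpoints use the worst pain score, which has its own rule.

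A reader might also infer that the arm summaries will be biased. The documents do not support this, because nothing shows that item completeness differs by arm or over time.

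Nor does the pain severity index share the fault. It has no partial-form allowance, so under section 4.3 it is missing if any of its four items is missing, which is coherent. With four complete items, a sum and a mean differ only by a constant factor.

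**Conclusion.** The point holds as a minor error of definition. As written, the function interference index mixes scores with maxima of 40, 50, 60 and 70. It understates partial forms by 14%, 29% or 43% for 6, 5 or 4 answered items. These percentages assume equal item scores and a literal reading without proration. The 43% applies to a single form with the fewest permitted answers and is not an estimate of bias in any reported result. The effect on group summaries cannot be sized from the SAP, because it gives no rate of partial forms. No conclusion of the trial rests on this index, so the change is desirable but not pressing.

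**What to change.** In section 6.2.3.1.1, define the function interference index as the mean of the answered interference items when at least 4 of the 7 are answered, and as missing otherwise. To keep the 0 to 70 scale, multiply that mean by 7; complete forms then keep exactly the score they have now.

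The cost is one line in the derivation and no new data. There is one small downside: the rule assumes that a subject's unanswered items equal the average of that subject's answered items. State this as an exception under section 4.3. Leave the pain severity index as it is.

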6.3 Pharmacokinetics / pharmacodynamics

Not applicable.

6.4 Safety

No formal statistical tests will be done for the safety endpoints.

A safety analysis will be performed at the same time as the final primary endpoint analysis. This analysis will include treatment-emergent safety events as of database closure for primary endpoint completion.

An updated analysis of safety events will be performed after the last followed patient completes active follow-up 2 years following the last dose of radium-223 dichloride treatment, which will be reported in a separate document from the Clinical Study report. In addition, safety events emerging during long-term follow-up conducted as part of this study will be reported in separate document(s) from the study Clinical Study Report.

6.4.1 Adverse events

All adverse events (AE) will be coded according to the latest Medical Dictionary for Regulatory Activities (MedDRA) Version as of database lock for the applicable analysis. The MedDRA version used will be documented in the CSR. The intensity of an AE will be documented using the NCI-CTCAE v4.03.

Adverse Events of Interest

A summary table and a listing will be provided for subjects who experienced following adverse events: pancytopenia and myelotoxicity including myelodysplastic syndrome, aplastic anemia and myelofibrosis. The events will be identified by medical reviewer based on verbatim recorded in database.

Treatment Period Analyses

The treatment period for this study, for purposes of safety analyses, extends from the initiation of study treatment until 30 days after the last administration of radium-223 dichloride.

Pre-treatment AEs

Pre-treatment AEs will be defined as AEs that started and either stopped before the first dose of study treatment or continued after and did not worsen in intensity (i.e. increase in CTCAE toxicity grade or became serious) during the treatment period.

Treatment-emergent AEs

All AEs starting or worsening within the treatment period will be considered TEAEs,

Post-treatment AEs

Post-treatment follow-up AEs will be defined as AEs that started after the treatment period. Note that the intention of this study is that only treatment-related AEs will be collected after the treatment period.

An overall summary of AEs will be provided to present the number and percentage of subjects with

- any pre-treatment AEs TEAEs, or post-treatment AEs
- any study treatment related TEAEs
- any serious TEAEs,
- any serious treatment related TEAEs
- any CTCAE Grade ≥ 3 TEAEs
- any TEAEs leading to drug modification or discontinuation
- any TEAEs leading to death
- any AEs leading to drug modification or discontinuation

TEAEs and post-treatment AEs will be summarized by MedDRA system organ class and preferred term. For each subject, multiple occurrences of the same event will be counted once within a system organ class and preferred term. For post-standard treatment AE tables, only treatment-related AEs, serious treatment-related AEs will be reported. Subjects who received 6 or less doses from Arm A and C versus subjects received 7 or more doses in Arm C will also be summarized for evaluating potential cumulative toxicity of extended regimen.

The same summaries will be repeated for related TEAEs, serious TEAEs, serious related TEAEs, CTCAE Grade ≥ 3 TEAEs, TEAEs leading to drug modification or discontinuation, TEAEs leading to death and any AEs leading to drug modification or discontinuation.

The maximum severity of the TEAEs and post-treatment AEs will be summarized according to the NCI-CTCAE toxicity criteria. For each subject, multiple occurrences of the same event will be counted once at their maximum severity within a system organ class and preferred term. TEAE will also be summarized by NCI-CTCAE toxicity criteria and relationship to study medication.

The numbers of subjects experiencing TEAEs will be presented.

The analysis of TEAEs will be reported by treatment group as treated (Arm A, Arm B, and Arm C).

Long-Term Follow-Up AEs

Long-term follow-up AEs are AEs arising during the long-term follow-up period. LTFU AEs will not be included in safety analysis summary tables for this study, but will be included in listings.

AE Listings

Data listings will be produced for all AE recorded in the study. Verbatim descriptions and coded terms will be listed for all AEs.

Serious adverse events (SAEs), deaths, AEs leading to discontinuation and AEs of interest will each have a separate listing.

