HEOR	Health Economics, Outcomes & Reimbursement
IBW	Ideal Body Weight
ICH	International Committee on Harmonization
ID	Identifier
INN	International Non-proprietary Name
ITT	Intent-to-treat
IV	Intravenous

IVRS/IWRS	Interactive voice/web response system
IXRS	Interactive response system (independent of type)
JSRC	Joint Safety Review Committee
kBq	Kilobecquerel
LCL	Lower Confidence Limit
LTFU	Long-Term Follow-Up
LTFUAE	Long-Term Follow-Up Adverse Event
MedDRA	Medical Dictionary for Regulatory Activities
MRI	Magnetic resonance imaging
NCI	National Cancer Institute
NCCN	National Comprehensive Cancer Network
NIS	Non-interventional Study
NIST	National Institute of Standards and Technology
nMiss	Number of missing values
OS	Overall survival
PC	Prostate cancer
mPCWG2	Modified Prostate Cancer Working Group 2
PRO	Patient Reported Outcomes
PSA	Prostate specific antigen
PT	Preferred Term
QoL	Quality of Life
Ra-223	Radium-223 dichloride
rPFS	Radiological progression free survival
SAE	Serious Adverse Event
SAF	Safety
SAP	Statistical Analysis Plan
SD	Standard Deviation
SMQ	Standardized MedDRA Queries
SOC	System Organ Class
SOP	Standard Operating Procedure
SSE	Symptomatic skeletal event
SSE-FS	Symptomatic skeletal event free survival
Std	Standard Deviation
TAS	(Bayer) Therapeutic Area (Oncology) Standards
TBW	Total Body Weight
TEAE	Treatment-Emergent Adverse Event
TTP	Time to progression
uCi	Microcurie
UCL	Upper Confidence Limit
W12	Week 12
W24	Week 24
WHO	World Health Organization
WHO-DD	World Health Organization Drug Dictionary

1. Introduction

Protocol 16507 is a 3-arm, randomized, open-label Phase II study to compare the efficacy and safety of a “standard dose” regimen of radium-223 dichloride with, a “high dose” regimen and an “extended dose” regimen, in subjects with castration-resistant prostate cancer metastatic to bone .

The study's 3 arms are:

- Arm A: 6 doses of 50 kBq/kg (55 kBq/kg after implementation of NIST update) radium-223 dichloride every 4 weeks ("standard" dose regimen)
- Arm B: 6 doses of 80 kBq/kg (88 kBq/kg after implementation of NIST update) radium-223 dichloride every 4 weeks ("high dose" regimen)
- Arm C: 12 doses of 50 kBq/kg (55 kBq/kg after implementation of NIST update) radium-223 dichloride every 4 weeks ("extended dose" regimen)

The study's co-primary endpoints are:

- Symptomatic skeletal event free survival from randomization (SSE-FS1) for the "standard dose" vs. "high dose" comparison (Comparison 1).

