4.4 Interim Analyses and Data Monitoring

No interim analysis for efficacy is planned.

A Joint Safety Review Committee (JSRC) will perform monitoring for safety and protocol compliance. The JSRC will meet at regular intervals as specified by the JSRC charter, approximately every 6 months, and may decide to meet more frequently. The JSRC will be supported by an independent Statistical Analysis Center (SAC) as specified in the Charter. Reports to the JSRC will be specified in a separate document.

The conduct of the JSRC is generally similar to a Data Monitoring Committee, except that membership may include sponsor, investigator, and/or independent members, and interim results of this open-label trial may be disclosed to the sponsor. Further details are described in the JSRC charter.

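### The marrow adverse events of interest are selected by a medical reviewer from verbatim text, with no fixed MedDRA term list and no stated masking to arm

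*SAP*

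**What the plan says.** The paragraph on adverse events of interest in SAP section 6.4.1 has three parts.

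- **Output:** "A summary table and a listing will be provided for subjects who experienced following adverse events". The sentence names no split by arm and no time window.
- **Scope:** "pancytopenia and myelotoxicity including myelodysplastic syndrome, aplastic anemia and myelofibrosis". Specific diagnoses are named, but the word *including* leaves the myelotoxicity category open.
- **Method:** "The events will be identified by medical reviewer based on verbatim recorded in database".

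The same section opens with the coding rule: "All adverse events (AE) will be coded according to the latest Medical Dictionary for Regulatory Activities (MedDRA) Version as of database lock". The introduction describes the design: "Protocol 16507 is a 3-arm, randomized, open-label Phase II study".

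The two supplements (July and October 2018) refer safety back to the main SAP. Each adds analyses under the heading of adverse events of interest, but these concern fractures. Neither supplies a term list, a case definition or masking for the marrow events.

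**The concern.** The trial compares a higher-activity regimen and a longer regimen with standard dosing, and the SAP itself singles out marrow events for a separate display. That display needs a stable definition, so that a subject in one arm is counted by the same rule as a subject in another.

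As written, the rule is one person's reading of free text. For a report of myelodysplastic syndrome the decision is easy. For other marrow reports that might or might not count as myelotoxicity, the SAP gives no criterion. In an open-label trial the reviewer may know the arm or the number of injections when deciding, and nothing in the SAP prevents that. Section 6.4 also plans safety reporting twice, at the final analysis and in a later update, and no rule carries the same selection from one to the other.

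What is at stake is whether one focused safety table is reproducible and even-handed. No hypothesis test depends on it.

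**Working it through.** The SAP gives no expected count or rate for these events, so there is no planned figure to reproduce. The check is mainly a comparison of what the sections state.

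**1. Is the selection rule fixed?** Section 6.4.1 names the actor (a medical reviewer) and the source (verbatim text). It does not give a term list, a query, a definition of myelotoxicity, a date relative to database lock, or masking. Two reviewers could follow the sentence faithfully and produce different tables.

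**2. Was a fixed rule available?** Yes. All adverse events are coded in MedDRA under the same section, so a list of preferred terms could be applied by program. SMQ is defined in the abbreviations but not used in the safety section. That shows nothing about intent, and the point does not need it.

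**3. Which outputs depend on the selection?**

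| Output (SAP section) | Depends on the reviewer's selection? |
|---|---|
| Summary table and listing of adverse events of interest (6.4.1) | Yes |
| TEAEs and post-treatment events by system organ class and preferred term (6.4.1) | No |
| Related, serious, Grade 3 or higher, discontinuation and death tables; maximum CTCAE grade (6.4.1) | No |
| Subjects with 6 or fewer doses versus 7 or more (6.4.1) | No |
| Hematology graded from laboratory values, shift tables and box plots (6.4.3) | No |
| Full listing with verbatim and coded terms (6.4.1) | No |

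**4. Do the unaffected outputs replace the affected one?** Only in part. The coded tables show each preferred term separately. The laboratory grades use measured values only, so they do not identify a diagnosis such as myelodysplastic syndrome. The table of adverse events of interest is the one planned output that brings these marrow events together as a group.

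**5. Scale of one decision.** Section 3.4 plans 360 subjects at 1:1:1, so 360 / 3 = 120 per arm. Assuming that all 120 are treated and form the denominator:

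- one subject included or excluded: 1 / 120 = 0.83 percentage points in that arm's rate;
- three subjects, all in the same direction: 3 / 120 = 2.5 percentage points.

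One to three decisions therefore move an arm's rate by 0.8 to 2.5 points. How many borderline reports will arise is not known from the SAP. With no test planned for safety (section 6.4), there is no error rate to compute.

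**The case against.** The best defence is that the safety comparison across doses does not rest on this table. Pancytopenia, myelodysplastic syndrome, aplastic anemia and myelofibrosis reported as TEAEs appear in the coded tables whatever the reviewer decides, and hematology is graded by arm from laboratory values. The full listing shows verbatim and coded terms side by side, so a reader can compare it with the listing of adverse events of interest and see what was included or left out. Verbatim review can also catch cases that coding misses. All of this stands, and it limits the point to one table and one listing. It does not close the gap: with no stated rule there is nothing to check the selection against, and the open category stays undefined.

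Three stronger readings are tempting, and the SAP supports none of them.

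- *The selection is made unblinded.* The SAP does not say what the reviewer sees. Section 4.4 does allow that "interim results of this open-label trial may be disclosed to the sponsor", but that concerns reporting through the safety review committee, not the selection of these events. Only the absence of stated masking can be claimed.
- *The dose-toxicity analysis as a whole depends on this judgement.* It does not, as the table of outputs shows.
- *A few decisions could create or hide a dose relation.* This needs event counts that the SAP does not give. With assumed counts of 7 on high dose and 4 on standard dose, the ratio is 7/4 = 1.75; dropping two high-dose reports gives 5/4 = 1.25, and adding two gives 9/4 = 2.25. These figures show how sensitive small counts are. They do not show likely bias, because they move one arm in one direction and leave the other untouched.

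**Conclusion.** The point holds in a narrow form. The SAP sets a selection method for the marrow adverse events of interest that is discretionary, has no term list, and has no stated masking to arm or injection count in an open-label trial. The one summary table and listing that group these events therefore cannot be regenerated from the coded data. Each discretionary decision moves an arm's rate by about 0.8 percentage points, assuming 120 treated subjects per arm; the number of such decisions is unknown. No test, no primary or secondary efficacy result and no other safety summary is affected. Severity is minor: a prespecification gap that is cheap to close.

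**What to change.** Add an appendix to the SAP that defines the marrow events of interest by MedDRA preferred terms or a named SMQ, including which terms count as myelotoxicity. Fix it before database lock and apply it by program to all arms, in both the final and the updated analysis. Because the coding version is the latest one at each database lock, record the version on which the list is based and document any term changes between the two analyses.

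Keep verbatim medical review as a supplement only. Carry it out on a listing without arm or number of injections, and show the added cases separately from those found by the list.

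The cost is one appendix, one query and one masked listing. The downside is that a fixed list may bring in a few non-specific terms that a clinical reader would have left out; the listing lets readers see them.

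### Section 6.4.1 classes a pre-existing AE that first worsens more than 30 days after the last dose as pre-treatment, which keeps it out of the main AE tables

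*SAP*

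**What the plan says.** SAP section 6.4.1 sets one window and three AE classes.

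- **Treatment period:** it "extends from the initiation of study treatment until 30 days after the last administration of radium-223 dichloride".
- **Pre-treatment AE:** began before the first dose and either stopped before it or "continued after and did not worsen in intensity (i.e. increase in CTCAE toxicity grade or became serious) during the treatment period".
- **TEAE:** "All AEs starting or worsening within the treatment period will be considered TEAEs".
- **Post-treatment AE:** "Post-treatment follow-up AEs will be defined as AEs that started after the treatment period".

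The section adds that the study's intention is that "only treatment-related AEs will be collected after the treatment period".

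The SOC/PT tables cover TEAEs and post-treatment AEs. So do the severity tables: "The maximum severity of the TEAEs and post-treatment AEs will be summarized according to the NCI-CTCAE toxicity criteria". Pre-treatment AEs appear in the overall summary and in the listing of all recorded AEs. The section also plans a summary of subjects with 6 or fewer doses (Arms A and C) against Arm C subjects with 7 or more, to look for cumulative toxicity of the extended regimen.

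**The concern.** The TEAE definition names starting and worsening as two separate routes into the class. The post-treatment definition has only the first route. The pre-treatment definition excludes worsening only if it happens during the treatment period. An event that was present at entry and worsens after the period closes is thus not merely left without a class. It fits the pre-treatment class, which describes what the subject brought to the trial.

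Marrow toxicity is a named AE of interest in section 6.4.1, and worsening of a cytopenia already present at entry is one form it can take. Because only treatment-related AEs are meant to be collected after the period, a late worsening that is recorded would tend to be one judged related to study drug. It would still carry the pre-treatment label and stay out of the tables that readers use to compare arms. The window is also longer with more doses, so the gap opens later in Arm C than in the 6-dose arms. That bears on the planned summary by number of doses.

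**Working it through.** **Inputs**

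- Arm A (SAP section 1): "Arm A: 6 doses of 50 kBq/kg (55 kBq/kg after implementation of NIST update) radium-223 dichloride every 4 weeks". Arm B also has 6 doses every 4 weeks.
- Arm C (SAP section 1): "Arm C: 12 doses of 50 kBq/kg (55 kBq/kg after implementation of NIST update) radium-223 dichloride every 4 weeks".
- Close of the treatment period: last dose + 30 days (section 6.4.1).
- Assumptions: no dose delays; days counted from the first dose as day 0; worsening kept on the original AE record.

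**The plan's own figure.** Section 3.4 puts last treatment at 44 weeks (10.12 months). With 12 doses the last is at (12 − 1) × 4 = 44 weeks, and 44 × 7 / 30.4375 = 10.12 months. It reproduces.

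**Close of the period after n doses** = 28 × (n − 1) + 30.

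- 6 doses (full course, Arms A and B): 28 × 5 + 30 = day 170 (24.3 weeks)
- 8 doses: 28 × 7 + 30 = day 226
- 9 doses: 28 × 8 + 30 = day 254
- 12 doses (full course, Arm C): 28 × 11 + 30 = day 338 (48.3 weeks)
- Full-course difference: 338 − 170 = 168 days = 24 weeks

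**The definitions applied to test cases**

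| Event | 6 doses (Arm A, B, or C stopped at 6) | 12 doses (Arm C) |
|---|---|---|
| Present at entry, worsens day 100 | TEAE | TEAE |
| Present at entry, worsens day 240 | pre-treatment | TEAE |
| Present at entry, worsens day 400 | pre-treatment | pre-treatment |
| New onset day 240 | post-treatment | TEAE |
| New onset day 400 | post-treatment | post-treatment |

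The day-240 rows separate two effects. Both the worsening and the new-onset event carry different labels by number of doses. For new onset, however, both labels are classes that the SOC/PT and severity tables cover. For the worsening event, the 6-dose label is one they do not cover. At day 400 the worsening event is outside those tables whatever the number of doses.

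**With post-treatment AEs widened to include later worsening:** the day-240 event becomes post-treatment after 6 doses and stays a TEAE after 12. The day-400 event becomes post-treatment in both.

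**Maximum severity.** Section 6.4.1 does not say over which period an AE's maximum grade is taken. An AE that starts at low grade on treatment and worsens after the period closes could therefore enter the TEAE severity table at its late grade. Late worsening would then be credited to treatment for one kind of event and to the time before treatment for the other.

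**The case against.** Four objections have weight.

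1. **Other outputs retain the event.** A reader might infer that late toxicity is lost. The SAP does not support that. New AEs after the period are post-treatment AEs. The worsened event stays in the all-AE listing and the overall summary. If serious or an AE of interest, it has a further listing, and the AE-of-interest table states no period limit. Laboratory values are graded independently of AE class (section 6.4.3). This stands. These outputs are not full substitutes, though: listings give no rates, and the laboratory tables carry no causality assessment and omit non-laboratory events.

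2. **The arm difference comes from the window, not the gap.** A period tied to the last dose gives different labels to new-onset events too, and at day 240 a 12-dose subject is still on treatment. Relative to the last dose the rule is the same in every arm. This stands for the label. It does not explain why only the 6-dose worsening falls outside the main tables.

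3. **Not every comparison is affected.** A reader might infer that both dose comparisons are distorted. On schedule, full-course subjects in Arms A and B both close at day 170, so A versus B is untouched. Nor does every Arm C subject differ: for a worsening at day 240 to be a TEAE, at least 9 doses are needed (day 226 after 8, day 254 after 9). Section 3.4 expects only 132.8 of 240 subjects in Arms A and C to be eligible at 24 weeks, about 66 per arm. No formal safety tests are planned (section 6.4).

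4. **Data collection may close the gap.** If a grade increase opens a new AE record with its own start date, the event has started after the period and is post-treatment. The SAP states no such rule, so the point is conditional. Conditions present at entry may also be recorded mainly as medical history, which would leave few pre-treatment AEs.

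**Conclusion.** The point holds in a limited form. If worsening stays on the original record, section 6.4.1 gives the wrong class to an AE that was present at entry and first worsens after the treatment period. The consequence is absence from the SOC/PT and maximum-severity tables, not from the study report.

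For full-course subjects on schedule, the tabulation differs by number of doses from day 170 to day 338. It affects comparisons with Arm C, including the summary of 6 or fewer against 7 or more doses. There the omission falls on the 6-dose side and could make an Arm C excess look larger than it is.

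The number of subjects affected cannot be computed: the SAP gives neither the frequency of AEs ongoing at entry nor the rate of late worsening. The change is worth making because the rule as written is wrong and cheap to correct. The documents do not support calling the effect large.

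**What to change.** Amend section 6.4.1 in three places.

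- **Post-treatment AEs:** those that started, or that worsened in CTCAE grade or became serious, after the treatment period.
- **Pre-treatment AEs:** among those still ongoing at the first dose, only those that do not worsen at any time after it.
- **Maximum-severity tables:** take each AE's highest grade within the period that the table covers.

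Also state whether a grade increase is held on the original AE record or opens a new one, since the derivation depends on it.

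The cost is SAP wording and derivation code, with no new data collection planned. If the CRF holds a single worst grade per AE with no date of change, laboratory dates or the date the event became serious would have to supply the split by period.

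The label difference between 6 and 12 doses will remain, because the period is tied to the last dose. The 6-dose event will, however, then belong to a tabulated class. Section 6.4.1 limits what it calls post-standard treatment AE tables to treatment-related events. If that means the post-treatment tables, the event will appear there only when judged related, and the amendment should say so.
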